6.0 Enrollment/Randomization

Following baseline assessments, patient-caregiver dyads ($N = 50$) will be randomly assigned to the ACT intervention or education/support condition in a 1:1 ratio using a stratified block randomization scheme to balance the groups by patient performance status (Eastern Cooperative Oncology Group scores 0 or 1 vs. 2).^{48, 50} We will stratify randomization by performance status because the decision to provide chemotherapy and other cancer treatments is often based on performance status.⁵¹ Randomization will be performed using a SAS procedure routinely employed by the IU Biostatistics Department. The study statistician will create the randomization procedure, and the PI will inform study therapists of their assigned patients. Other members of the study team will remain blind to participants' group assignment. All patients will be registered with the Indiana University Cancer Center Clinical Trials Office. Applicable regulatory documents must be completed and on file prior to registration of any patients.

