All potential participants will be informed as to their rights as volunteers in a research study and will provide informed consent for research participation. The key elements of the informed consent procedure which will be explained to prospective participants are: 1) the research status of the study; 2) the potential risks and the provisions for them; 3) the lack of guarantee of benefit from participation; 4) the voluntary nature of the study; 5) the lack of consequence to medical care of the decision to consent or refuse to participate; and 6) the freedom to withdraw from the study or to refuse to answer specific questions or to participate in any aspect of the study at any time. Consenting patients and caregivers will have the option of providing the name and contact information for an emergency contact person who may be contacted in the event that the study team repeatedly cannot reach the participant (see Appendix R for contact information sheets).

Inclusion of Women and Minorities

We will recruit advanced GI cancer patients and their primary family caregivers. According to American Cancer Society statistics,¹ 57% of GI cancers are expected to be diagnosed in men in 2019. Thus, we expect approximately 60% of our patient sample to be male. Evidence indicates that the majority of cancer patients' family caregivers are women;⁵³ indeed in our pilot work, 66% of caregivers of advanced GI cancer patients were women.⁵⁴ Thus, we expect approximately 65% of our caregiver sample to be female. No racial or ethnic group will be excluded from study participation. We will oversample racial and ethnic minorities to generate a sample representative of Indianapolis and surrounding areas. Eskenazi Health—one of our recruitment sites—sees a highly racially and ethnically diverse patient population. Based on recent data from the study sites, we anticipate that the final sample will be approximately 70% non-Hispanic White, 20% non-Hispanic Black or African American, 6% Hispanic, and 4% Asian or members of other racial/ethnic groups.

Interview Procedures

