Session 6 (dyadic): Review and other resources	
 • Review all topics discussed in prior sessions and available resources for addressing each topic area • Discuss websites for accessing cancer-related info HW6: Review handouts summarizing all resources

Training of Therapists and Treatment Fidelity

Training of therapists will involve didactics, live demonstrations, and role plays developed by the PI and her collaborators. All intervention sessions will be audio recorded, and the PI and [name] (study co-investigator and licensed clinical psychologist) will randomly review 20% of recorded sessions to ensure fidelity and quality control. The PI will use therapist adherence checklists for the ACT and education/support conditions adapted from NIH-funded trials with cancer patients (see Appendix P).⁷³ The PI and [name] will provide ongoing supervision of therapists. During individual supervision with therapists, which will occur

approximately every 1-2 weeks, treatment adherence scores will be provided and treatment fidelity issues discussed. Role-plays will be conducted to correct deviations from study procedures.

Protection of Human Subjects

The protocol has several measures to monitor for, respond to, or minimize potential distress or anxiety detailed below. However, it is important to place the risk of distress in perspective. Based on survey evaluations by cancer patients and caregivers enrolled in other psychosocial studies,^{52, 62} participants should not find the questions or the time requirements of the study to be burdensome. In fact, a large proportion of individuals who have participated in similar studies have commented that they felt that they have benefited from sharing their experiences and taking part in interventions. Thus, the risk of distress is modest and the safeguards detailed below should be adequate.

- Study team members will clearly acknowledge the voluntary nature of participation and individuals will have the ability to decline further contact from study personnel (i.e., to opt out).
- The research assistant, qualitative interviewer, and study therapists will receive training from [name], a clinical psychologist with extensive clinical and research experience with medical populations. This training will include ways to identify and respond to signs of distress.

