10.0 Study Withdrawal/Discontinuation

Criteria for removal from the study are as follows:

- Observed severe cognitive impairment that renders continued participation in the study impossible, such as confusion or impaired ability to read or to provide accurate answers to the interviewer.
- The patient consents to participate in the study, but their family caregiver declines study participation or is not eligible for this study. The patient would no longer be eligible to participate in this study, as we are interested in examining data from patient-caregiver dyads.
- If the patient or caregiver is no longer able to participate in this study due to death or medical factors or decides to stop participation, then the other member of the dyad (patient or caregiver) will no longer be eligible to participate in this study.
- The participant expresses significant distress related to completion of the study (the PI will refer the participant to clinical services if needed).
- The participant provides verbal or written notification that she has decided to discontinue study participation.
- The participant does not follow the study rules (e.g., repeatedly does not answer the phone to complete a scheduled interview).
- Any other reason for which the principal investigator believes the participant should be withdrawn.

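### Repeated unanswered calls for one interview can remove a randomised participant from the whole study, losing a 3-month outcome that might still have been collected

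*Combined protocol and SAP*

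**What the plan says.** Section 10.0 opens its list with "Criteria for removal from the study are as follows", so the criteria end study participation and not only the sessions. Two items need no decision by the participant:

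- "The participant does not follow the study rules (e.g., repeatedly does not answer the phone to complete a scheduled interview". No number of attempts is given and no decision-maker is named.
- "Any other reason for which the principal investigator believes the participant should be withdrawn". Here the decision-maker is the PI, and no criteria are given.

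Neither item is confined to the time before randomisation. No section says that a removed participant is still offered the remaining assessments.

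On knowledge of the arm, Section 6.0 says "the PI will inform study therapists of their assigned patients. Other members of the study team will remain blind to participants' group assignment". Section 7.0, on therapist training and fidelity, adds "The PI will use therapist adherence checklists for the ACT and education/support conditions". The PI therefore knows the assignment.

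On timing, Table 1 in Section 5.0 sets both follow-up assessments by reference to the last intervention session. Neither depends on the other having been done. Both are carried out by interviewers blinded to arm.

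Before removal, Section 7.0 provides a letter after several failed attempts and an optional emergency contact. Section 11.0 provides a repeated-measures mixed model, multiple imputation with 50 imputed samples, and tracking of reasons for dropout. It defines no analysis population and no sensitivity analysis for removals made by staff.

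**The concern.** A missed interview is ordinary non-response: one value is missing and the next can still be sought. Section 10.0 allows it to become an exit from the study, after which the 3-month primary, secondary and healthcare-use outcomes are not sought either. The people most exposed are those whom the trial selects. Patients enter with moderate to severe fatigue interference, and caregivers enter with significant burden or distress. Someone too fatigued or too burdened to take repeated calls at 2 weeks is plausibly different on the primary outcome at 3 months.

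Aim 2 is meant to deliver effect-size estimates, and the findings are meant to inform a larger trial. Bias in those estimates, and attrition produced by the protocol's own rule, would both carry over into that planning.

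The catch-all criterion raises a second, weaker issue. It gives open-ended discretion over randomised participants to someone who knows the arm, and it asks for no record that would let a reader see afterwards whether removals differed by arm.

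**Working it through.** **Does removal cost data that could be had?** Inputs are from Table 1.

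- 2-week assessment: target 2 weeks after the last session, with up to 14 days' delay allowed. The window closes 2 + 2 = 4 weeks after the last session.
- 3-month assessment: target 3 months (about 13 weeks) after the last session, from 7 days before. The window opens at about 13 − 1 = 12 weeks.
- Gap: about 12 − 4 = 8 weeks.

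A participant who was unreachable throughout the 2-week window may well be reachable some 8 weeks later. Removal forgoes that attempt.

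**How large could the effect on an estimate be?** The plan attaches no figure to removals, so there is none to reproduce. What follows is an illustration on stated assumptions.

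- From the documents: 50 dyads randomised 1:1, so n = 25 patients and 25 caregivers per arm. The pilot between-group effects quoted in Section 1.0 are −.30 (full sample) and −.59 (moderate to severe subsample).
- Assumed: k = 2 or 4 removed in one arm and none in the other. Their mean differs from those kept by g = 0.5 or 1 SD.
- Formula: full-arm mean = kept mean + (k/n) × g, so the complete-case shift is (k/n) × g.

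| k | g = 0.5 SD | g = 1 SD |
|---|---|---|
| 2 | 2/25 × 0.5 = 0.04 | 2/25 × 1 = 0.08 |
| 4 | 4/25 × 0.5 = 0.08 | 4/25 × 1 = 0.16 |

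Against the pilot effects, 0.04/0.30 = 13% and 0.16/0.30 = 53%; 0.04/0.59 = 7% and 0.16/0.59 = 27%. If 15% attrition has already reduced the arm to 21 (25 × 0.85 = 21.25), the range is 2/21 × 0.5 = 0.05 to 4/21 × 1 = 0.19 SD.

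Three features make these figures generous:

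- They are complete-case figures. The mixed model and the imputation use the observed scores and would reduce the shift. For someone missed at 2 weeks, though, the only earlier outcome score is the baseline one.
- Similar removals in both arms would tend to cancel.
- They treat every removed participant as someone who would have answered at 3 months. If only half would have, about half the shift is avoidable.

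**Is power the issue?** Hardly. With 21 per arm the detectable effect at 80% power is d = 0.886. With four further losses in one arm (17 against 21) it is 0.94. The concern is bias and avoidable missingness.

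**The case against.** The strongest reply is that the rule is narrower than it looks and that the plan already softens it. Much of that stands.

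- A reader might infer that one missed call, or simply one missed interview, ends participation. The text does not support this: it requires repeated non-answer, and a letter is sent after several attempts. What remains is that repeated non-answer for a single scheduled interview is enough.
- A reader might infer that the unblinded PI decides on removal for missed calls. That item names nobody, and the follow-up calls are made by blinded interviewers. Only the catch-all names the PI.
- A reader might infer that removals will depend on arm or outcome. No section says so. The PI may audit interview recordings, but so may another trained team member, the purpose is protocol adherence, and a missed interview leaves no recording. Arm-related removal is a possibility left open.
- A reader might see a conflict with the consent terms, which give freedom "to refuse to answer specific questions or to participate in any aspect of the study at any time". Those terms do not say that refusing one part preserves enrolment, so no contradiction is shown.
- A reader might infer that the rule distorts the feasibility criterion. For the missed-interview route it does not. That criterion requires all assessments, and a dyad that misses the 2-week interview has already failed it. Only descriptive attrition changes.
- A reader might infer that the partner is always lost too. The partner rule, "then the other member of the dyad (patient or caregiver) will no longer be eligible to participate in this study", follows death, medical factors or a decision to stop. Removal by staff is not listed as a trigger.

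The plan also undertakes to track participation and to seek reasons for dropout. That helps interpretation, but it neither brings back a 3-month outcome that nobody tried to collect nor records who decided on a removal. Multiple imputation in its usual form assumes missing at random, which removals resting on unrecorded judgement may not satisfy.

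**Conclusion.** The point holds in a limited form. As written, Section 10.0 lets repeated non-response to one interview end all outcome follow-up, and so forgoes 3-month data that the schedule would otherwise allow to be collected. This is avoidable and possibly informative missingness in the Aim 2 estimates, and it inflates descriptive attrition. The link between missed calls and outcome is plausible from the eligibility criteria but is not shown in the documents.

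The size is unknown. The 0.04 to 0.16 SD range rests on assumed numbers removed (2 to 4 of 25), removal in one arm only, an assumed gap of 0.5 to 1 SD, and a complete-case comparison. The planned analysis would give less. The discretionary criterion is a secondary matter of transparency: the person holding it knows the arm, but the documents do not support a claim that it would be used according to arm.

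The change should be made, because the rule is explicit and its correction is cheap.

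**What to change.** In Section 10.0, reword the study-rules item so that repeated non-response to a scheduled interview counts as a missed assessment. State that the participant is still called at the next scheduled assessment unless consent has been withdrawn.

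For every removal initiated by staff, under either item, record the reason, the date and the decision-maker, and report these by arm. This extends the tracking of dropout reasons already promised in Section 11.0.

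Leave the distress criterion, the partner criteria and the PI's safety-related discretion as they are; nothing here gives grounds to alter them.

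The cost is a few lines of protocol text, a short log, and some calls that reach nobody. The letters and contact sheets needed are already in place.

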11.0 Statistical Considerations

Aim 1. Feasibility and acceptability will be evaluated via descriptive statistics for accrual, attrition, and adherence as well as Likert-scale items assessing intervention helpfulness. We will judge this trial as feasible if: 1) $\geq 60\%$ of screened eligible dyads enroll in the study;²¹ and 2) $\geq 70\%$ of enrolled dyads complete 5-6 intervention sessions and all assessments. We will judge this trial as acceptable if $\geq 70\%$ of dyads rate ACT as moderately to extremely helpful (i.e., an average score ≥ 4 on 1 to 5 Likert scale items).

To analyze qualitative data on ACT's acceptability, we will use an immersion/crystallization approach.⁸⁰ Research questions guiding the analysis pertain to the perceived helpfulness of ACT components and their impact on functioning and well-being. Interviews will first be transcribed by a trained research assistant. Analysis of the interview data will consist of two phases: open and focused coding.^{80, 81} In the open coding phase, the analysts (Drs. [name], [name], and a Ph.D. student in clinical psychology) will independently label each line of data to reflect meanings or themes emerging from the text. This is done iteratively, combining, adding, or eliminating themes, until analysts agree on a set of emergent thematic categories (codes). In focused coding, codes derived in open coding are independently applied to all transcripts. Special attention will be paid to negative cases (i.e., data that may call initial observations or interpretations into question).⁸² Transcripts will be divided evenly among analysts, with every fourth transcript coded in common to maintain consistency in coding over time. Analysts will meet bi-weekly to compare commonly-coded transcripts. Discrepancies will be resolved by consensus. Atlas-ti software will facilitate coding, and qualitative results will inform intervention refinement.

Aim 2. Given that this is a pilot study, our data analytic approach for Aim #2 will be to derive effect size estimates rather than test for statistical significance. A linear mixed-model repeated measures approach (SAS Proc-Mixed) will be used to examine ACT's effects on primary and secondary outcomes. For outcome measures that only patients or caregivers complete (e.g., patient fatigue interference or caregiver burden), models will include main effects of time (as categorical) and study group and the time-by-study group interaction. Treatment effects will be evidenced by the interaction between time and study group (i.e., group mean differences after the intervention but no such differences at baseline). Models will include random intercepts to account for nonindependence of individuals' scores across time. For outcomes reported by patients and caregivers (e.g., psychological flexibility), multilevel modeling for dyadic data will be used.^{83, 84} Models will include the main effects of time, study group, and social role (patient vs. caregiver) as well as all two and three-way interactions between these variables. The time x study group x role interaction will estimate the degree to which treatment effects are different for patients and caregivers. Dyadic models will include random intercepts for patients and caregivers, as well as the covariance between the intercepts to account for nonindependence across time and across partners.

Aim 3. To conduct data analyses for Aim #3, we will use logistic and Poisson regression models to explore the effects of ACT on patient and caregiver physical and mental health service use (e.g., number of patient ER visits, patient and caregiver use of counseling and/or psychiatric medication). Logistic and Poisson regression analyses are appropriate for binary and count outcome data, respectively. Analyses will examine study condition as a predictor of health service use over the entire study period, controlling for baseline service use. Support service referrals will be a covariate in analyses of mental health service use.

Statistical power. Although our analyses focus on effect sizes rather than statistical significance, we calculated power for comparing primary outcomes (patient fatigue interference and caregiver burden) between study groups. With a sample size of 34 patients and 34 caregivers at 2 weeks post-intervention (assuming 15% attrition), we will have 80% power ($\rho=.05$, two-tailed) to detect a large intervention effect ($d=.99$) on either primary outcome in a linear mixed model.⁸⁵ ACT had large effects on distress and QoL outcomes in late-stage ovarian cancer patients ($d=.89-1.69$) compared to CBT³³ and a medium effect ($d=-.59$) on fatigue interference compared to education/support in metastatic breast cancer patients with moderate-severe baseline fatigue interference.³⁴

Missing data. All data will be assessed for missingness and multiple imputation with 50 imputed samples will be used.⁸⁶ We will also compare participants and those who decline participation or withdraw on demographic and medical factors using t-tests and Chi-square analyses. Further, we will carefully track study participation and try to understand the reasons for dropout and missing data wherever possible. Identifying potential dropout and missing data mechanisms will allow us to incorporate those factors as auxiliary variables for multiple imputation as well as full information maximum likelihood estimation method assuming Missing at Random in our future Phase II trial.

Potential covariates. T-tests and chi-square analyses will be performed to identify any group differences in potential baseline covariates (e.g., demographic and medical variables), and if there are differences these variables will be used as covariates.

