In one trial, late-stage ovarian cancer patients were randomly assigned to 12 in-person sessions of ACT or 12 in-person sessions of CBT.³³ ACT participants showed large and significantly greater improvement in general distress ($d = .89$), global QoL ($d = 1.35$), anxiety ($d = 1.26$), and depressive symptoms ($d = 1.69$) than CBT participants over the intervention period. Notably, all attrition was due to death or beginning hospice; thus, ACT appeared to be feasible and acceptable to patients. Other pilot feasibility trials of ACT in cancer have also found positive changes in psychological outcomes.^{25, 31} For example, Feros and colleagues tested a 9-session ACT intervention for distressed patients with various cancers.²⁵ General distress, mood, and global QoL significantly improved immediately post-intervention and three months later compared to baseline. Effect sizes for general distress and mood were large, and the effect size for global QoL was medium. These pilot data suggest that ACT warrants further study in cancer. Indeed, our team extended prior pilot studies by using telephone-based ACT to target fatigue interference and related outcomes in 47 MBC patients.³⁴ The intervention showed strong evidence of feasibility and promise with respect to fatigue and sleep interference relative to an education/support condition. Regarding feasibility, the majority (64%) of patients who could be reached via phone were screened for eligibility, and 100% of eligible patients consented. Additionally, retention was good with 83% of the entire sample completing the 8-week follow-up, and 79% completing the 12-week follow-up. Fatigue interference showed moderate reduction across time in the ACT group and minimal change in the education/support group; the between-group effect size was -.30 at 12 weeks. Furthermore, when examining the subsample ($n = 24$) with moderate to severe fatigue interference at baseline, the between-group effect size was -.59 at 12 weeks. ACT participants also showed decreased sleep interference at 12 weeks, with a between-group effect size of -.40 in the full sample and -.61 in the subsample with moderate to severe fatigue interference. Differences between study conditions were not significant; however, because it was a pilot study, we focused our analyses on effect sizes rather than statistical significance.

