2.0 Study Objectives

Building on patient-focused ACT pilots in cancer,^{25, 33, 34} this NCI-funded pilot trial tests a novel, dyadic telephone-based ACT program for addressing both fatigue interference (i.e., fatigue's negative impact on activities, mood, and cognition) in advanced GI cancer patients and family caregiver burden. In order to enhance translation to geographically dispersed individuals and those with high symptom burden or functional impairments, we will deliver the intervention via phone. Advanced GI cancer patients with moderate to severe fatigue interference and their primary family caregivers with significant caregiving burden ($N=50$ dyads) will be randomized to six weekly 50-minute telephone sessions of either (1) ACT or (2) education/support. ACT includes acceptance and mindfulness meditation exercises, identification of personal values, and engagement in activities consistent with these values. Examples of dyadic intervention components include joint mindfulness practices and having each participant describe the other person's strengths and resources for goal achievement. Feasibility will be examined via accrual, attrition, and adherence rates, and acceptability will be evaluated using a mixed methods approach (qualitative and quantitative). Outcomes will be assessed at baseline, 2 weeks post-intervention, and 3 months post-intervention. Findings will inform an R01 application to conduct a large-scale RCT of intervention efficacy. The study objectives are:

2.1 Primary Objective: To evaluate the feasibility and acceptability of delivering telephone-based ACT to advanced GI cancer patients and their caregivers.

2.2 Secondary Objective: To test the effects of telephone-based ACT on patient fatigue interference and caregiver burden (primary outcomes) as well as patient sleep interference and patient and caregiver engagement in daily activities, progress in value-based living, psychological flexibility, and QoL (secondary outcomes).

Hypothesis: ACT will lead to improved primary and secondary outcomes as compared to education/support.

2.3 Exploratory Objective:

To explore the effects of telephone-based ACT on patient and caregiver physical and mental health service use (tertiary outcomes).

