Session 5 (dyadic) Detaching from Internal Experiences (Self as Context)	
 • Practice mindfulness (3-step self-compassion practice) with therapist • Exercises to promote observing and detaching from fatigue and emotions about cancer or caregiving to cultivate a transcendent sense of self from which to observe and accept changing experience HP5: Goal setting; practice value-based goal; daily mindfulness practice (person's choice on CD)
Session 6 (dyadic) Taking Steps to Do What Matters to You (Committed Action)	
 • Practice mindfulness (brief body scan exercise) with therapist • Recap of skills and what patient and caregiver learned • Goal setting around expanding values-consistent behavior into future • Termination and next steps in the study HP6: Continue written goals

Education/Support Condition Procedures

Dyads in the education/support arm will be directed to resources for practical and health information and contact information for psychosocial services. Thus, this study tests whether

ACT is superior to supportive listening and education on medical center and community resources, consistent with common interventions in clinical settings. The duration of sessions and number and order of dyadic vs. individual sessions will be identical to the ACT condition. A similar comparator was used in our ACT pilot trial with metastatic breast cancer patients,³⁴ and similar comparison groups have been used in studies with primarily advanced cancer patient-caregiver dyads.^{71, 72} A licensed therapist will deliver the

education/support intervention. Table 4 provides a summary of the topics for each education/support session, and the manual is found in Appendix N. While the therapist will aim to hold sessions on a weekly basis for 6 weeks, participants will have up to 12 weeks to complete the 6 sessions.

Education/support participants will complete the same weekly fatigue and distress assessments as those in the ACT condition. Sessions will include an orientation to the patient's medical center and treatment team, education regarding common QoL concerns and symptoms experienced by cancer

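### Completion is judged only on both arms pooled, so no threshold tests whether ACT itself can be delivered, which is the primary objective

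*Combined protocol and SAP*

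**What the plan says.** Section 2.1 gives the primary objective: "To evaluate the feasibility and acceptability of delivering telephone-based ACT to advanced GI cancer patients and their caregivers". Section 2.0 adds that the findings will inform an R01 application.

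Section 11.0 (Aim 1) turns this into rules. The sentence opening "We will judge this trial as feasible if" sets two conditions: at least 60% "of screened eligible dyads enroll in the study", and at least 70% "of enrolled dyads complete 5-6 intervention sessions and all assessments". Acceptability has its own rule, at least 70% "of dyads rate ACT as moderately to extremely helpful". Accrual, attrition and adherence are to be described, but the section does not say by arm.

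Section 6.0 states that the 50 dyads "will be randomly assigned to the ACT intervention or education/support condition in a 1:1 ratio". Section 7.0 says of education/support: "The duration of sessions and number and order of dyadic vs. individual sessions will be identical to the ACT condition".

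Two related places concern people who decline. Section 11.0 (Missing data) plans to compare them with participants on demographic and medical factors. Section 13.0 has the screening information of decliners and ineligible people destroyed after three months. Section 14.0 allows up to two years of data collection.

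**The concern.** Of the three thresholds, only acceptability names ACT, and a helpfulness rating is not a measure of completion. The completion rule is the one that would show whether patients and caregivers can get through the ACT programme, and half of the dyads it counts never receive ACT. The verdict on the primary objective can therefore be carried, or sunk, by the comparator. If the trial is called feasible on that basis, the R01 application would rest on a statement about ACT delivery that the rule did not examine.

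The records issue is separate and smaller. If decliners' data are destroyed on a rolling basis, the selection-bias comparison may lack its inputs at the final analysis, and destruction cannot be undone.

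**Working it through.** The plan gives no precision or pass probability for its feasibility thresholds, so there is no stated figure to reproduce first.

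**Inputs.** From the documents: 50 dyads and 1:1 allocation (section 6.0); a 70% completion threshold and a 60% accrual threshold (section 11.0). Assumed: exactly 25 dyads per arm, independent outcomes, and all true completion rates.

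**What the rule counts.** 70% of 50 is 35 completers. Reading the sessions as ACT sessions only does not work: ACT dyads are at most 25/50 = 50% of those enrolled, so 70% could never be reached. The pooled reading is the only workable one.

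**Splits that meet the pooled rule**
- 17 + 18 = 35: ACT 68%, control 72%.
- 14 + 21 = 35: ACT 56%, control 84%.

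**Pass probabilities.** Let X ~ Binomial(25, ACT rate) and Y ~ Binomial(25, control rate). The pooled rule passes with P(X + Y ≥ 35). An ACT-only 70% rule needs 0.70 × 25 = 17.5, so at least 18, and passes with P(X ≥ 18).

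| True ACT | True control | Pooled passes | ACT-only passes | Pooled passes with X < 18 |
|---|---|---|---|---|
| 60% | 60% | 9.6% | 15.4% | 3.6% |
| 60% | 70% | 27.9% | 15.4% | 16.2% |
| 60% | 85% | 72.3% | 15.4% | 57.0% |
| 70% | 70% | 56.9% | 51.2% | 15.4% |
| 80% | 80% | 96.9% | 89.1% | 8.8% |
| 80% | 60% | 57.0% | 89.1% | 1.2% |

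The third row shows the control arm carrying the verdict. The last row shows the reverse: ACT completion is truly 80%, yet the pooled rule fails 43% of the time.

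**Precision.** Wilson 95% intervals: 18/25 = 72%, 52% to 86%; 35/50 = 70%, 56% to 81%.

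**Accrual.** With 50 enrolled, 50/83 = 60.2% passes and 50/84 = 59.5% fails. At least 84 − 50 = 34 dyads must pass the screens and then decline before the accrual rule fails.

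**Decliners' records.** Section 7.0 (Recruitment Process) records for decliners, with permission, a reason, age, gender and race, plus relationship for caregivers. It records no medical factors. The only described source of medical factors for decliners is the screening information that section 13.0 destroys after three months.

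**The case against.** The strongest reply is that pooled completion is a proper measure of whether the trial can be run. Section 11.0 judges the trial, the control sessions match ACT in length, number and order, and a later RCT needs both arms to stay in. All of that stands. A reader might infer that the pooled rule is an error; the documents do not support that, and it should be kept. ACT is not ignored either: it has its own acceptability threshold, qualitative interviews and a therapist adherence checklist. None of these measures completion by the dyads assigned to it.

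A second reply is that the large figures need a wide arm gap. That also stands. The documents give no completion rates by arm, and with both arms at 60% a pooled pass with ACT below 18/25 occurs only 3.6% of the time. It would go too far to say that the trial is likely to mislabel ACT as feasible.

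Third, a reader might infer from sections 4.1, 4.3, 5.0 and 7.0 that every refusal leaves the accrual denominator, because willingness and a consenting caregiver are listed as eligibility criteria and a patient is told of ineligibility when the caregiver declines. The documents as a whole do not support this. The recruitment text treats decliners and ineligible people as separate groups, and section 1.0 separates the two when it reports of the team's earlier patient-only pilot that "100% of eligible patients consented". Decliners are most likely meant to stay in the denominator. What is open is the counting unit, since up to three caregivers may be screened per patient.

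Fourth, it is tempting to say that the decliner comparison will be impossible. Section 13.0 does not say whether the screening information includes the refusal reason and demographics, or when the three months start. Appendix S lists the screening form and refuser information together, but it also lists medical data sheets, so that grouping settles nothing. The text can be read to cover the refuser data; it does not clearly do so.

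**Conclusion.** The point holds for completion. Followed exactly, section 11.0 can return a feasible verdict with ACT completion below 70%, and can withhold one when ACT completion is high but control completion is low. That such splits satisfy or fail the rule is simple arithmetic, given about 25 dyads per arm. Their frequency is unknown: at true ACT completion of 60%, a pooled pass ranges from 10% to 72% across control rates of 60% to 85%, all of which are assumptions. The trial remains valid; what needs correcting is the match between the primary objective and its decision rule.

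The mismatch between the decliner comparison in section 11.0 and the destruction rule in section 13.0 is a secondary point to be reconciled. The accrual denominator needs only a minor clarification.

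**What to change.** **Completion (section 11.0).** Keep the pooled 70% rule as the verdict on trial conduct. Add a separate verdict on ACT delivery: feasible if at least 70% of dyads randomised to ACT complete 5 or 6 sessions and every assessment. State it as a percentage of the actual arm size, because stratified block randomisation does not guarantee 25 per arm (at 24, 17/24 = 70.8% would qualify). Report completion by arm with confidence intervals. The two verdicts should stay separate. A joint rule requiring both would still fail ACT because of the control arm: with ACT truly 80% and control 60%, it passes 56% of the time, against 89% for ACT alone.

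The cost is lower precision (52% to 86% at 18/25, against 56% to 81% at 35/50) and an ACT verdict that passes 51% of the time at true completion of 70% and 89% at 80%. The completion data are already collected.

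**Decliners' data (sections 11.0 and 13.0).** Keep, de-identified and until the final analysis, the reason, age, gender and race (plus caregiver relationship) already collected with permission, and limit the decliner comparison to the variables kept. This changes a privacy commitment, so the wording must be checked against the consent and authorisation forms.

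**Accrual (section 11.0).** Add one sentence: dyads that pass the screens and then decline stay in the denominator, and each patient counts once however many caregivers are screened.
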